
9.5.3 Appropriateness of Measurements

All clinical assessments are standard measurements commonly used in studies involving subjects with HCC.

The safety assessments to be performed in this study, including hematology analyses, blood chemistry tests, urinalysis, vital signs, ECGs, echocardiograms or MUGA scans, physical examinations and assessment of AEs, are standard evaluations to ensure subject safety.

9.5.4 Reporting of Serious Adverse Events, Pregnancy, and Events Associated with Special Situations

9.5.4.1 Reporting of Serious Adverse Events

All SAEs, regardless of their relationship to study treatment, must be reported on a completed SAE form as soon as possible but no later than 1 business day from the date the investigator becomes aware of the event.

SAEs, regardless of causality assessment, must be collected through 30 days after last dose or until the subject initiates new anticancer therapy, whichever is earlier. All SAEs must be followed to resolution or, if resolution is unlikely, to stabilization. Any SAE judged by the investigator to be related to the study drug or any protocol-required procedure should be reported to the sponsor regardless of the length of time that has passed since study completion.

The detailed contact information for reporting of SAEs is provided in the Attachment.

It is very important that the SAE report form be filled out as completely as possible at the time of the initial report. This includes the investigator or subinvestigator's assessment of causality.

Any follow-up information received on SAEs should be forwarded from the investigator to the sponsor within 1 business day of its receipt. If the follow-up information changes the investigator's assessment of causality, this should also be noted on the follow-up SAE form.

Preliminary SAE reports should be followed as soon as possible by detailed descriptions including copies of hospital case reports, autopsy reports, and other documents if requested by the sponsor.

9.5.4.2 Reporting of Pregnancy and Exposure to Study Drug Through Breastfeeding

Any pregnancy in which the estimated date of conception is either before the last visit or within 5 months of last study treatment or 30 days following the last study treatment if the subject initiates new anticancer therapy, whichever is earlier, and any partner's pregnancy of male subjects in which the estimated date of conception is either before the last visit or within 30 days of last study treatment or 30 days following the last study treatment if the

subject initiates new anticancer therapy, whichever is earlier must be reported. Also, any exposure to study drug through breastfeeding during study treatment or within 5 months of last study treatment or 30 days following the last study treatment if the subject initiates new anticancer therapy, whichever is earlier, must be reported.

If an adverse outcome of a pregnancy is suspected to be related to study drug exposure, this should be reported regardless of the length of time that has passed since the exposure to study treatment.

A congenital anomaly, death during perinatal period, an induced abortion, or a spontaneous abortion are considered to be an SAE and should be reported in the same time frame and in the same format as all other SAEs (see Reporting of Serious Adverse Events [Section 9.5.4.1]).

Pregnancies or exposure to study drug through breastfeeding must be reported by fax or email as soon as possible but no later than 1 business day from the date the investigator becomes aware of the pregnancy or breastfeeding. The contact information for the reporting of pregnancies and exposure to study drug through breastfeeding is provided in the Attachment. The Pregnancy Report Form must be used for reporting. All pregnancies must be followed to outcome. The outcome of the pregnancy must be reported as soon as possible but no later than 1 business day from the date the investigator becomes aware of the outcome.

A subject who becomes pregnant must be withdrawn from the study.

9.5.4.3 Reporting of Events Associated with Special Situations

9.5.4.3.1 REPORTING OF ADVERSE EVENTS ASSOCIATED WITH STUDY DRUG OVERDOSE, MISUSE, ABUSE, OR MEDICATION ERROR

Adverse events associated with study drug overdose, misuse, abuse, and medication error refer to AEs associated with uses of the study drug outside of that specified by the protocol. Overdose, misuse, abuse, and medication error are defined as follows:

Overdose	Accidental or intentional use of the study drug in an amount higher than the protocol-defined dose
Misuse	Intentional and inappropriate use of study drug not in accordance with the protocol
Abuse	Sporadic or persistent intentional excessive use of study drug accompanied by harmful physical or psychological effects
Medication error	Any unintentional event that causes or leads to inappropriate study drug use or subject harm while the study drug is in the control of site personnel or the subject.

All AEs associated with overdose, misuse, abuse, or medication error should be captured on the CRF and also reported using the procedures detailed in Reporting of Serious Adverse Events (Section 9.5.4.1) even if the AEs do not meet serious criteria. Abuse is always to be captured as an AE. If the AE associated with an overdose, misuse, abuse, or medication error does not meet serious criteria, it must still be reported using the SAE form and in an expedited manner but should be noted as nonserious on the SAE form and the CRF.

9.5.4.4 Expedited Reporting

The sponsor must inform investigator, the head of the medical institution, and regulatory authorities of reportable events, in compliance with applicable regulatory requirements, on an expedited basis (ie, within specific time frames). For this reason, it is imperative that the investigator provide complete SAE information in the manner described above.

9.5.4.5 Breaking the Blind

Not applicable.

9.5.4.6 Regulatory Reporting of Adverse Events

Adverse events will be reported by the sponsor to regulatory authorities in compliance with local and regional law and established guidance. The format of these reports will be dictated by the local and regional requirements.

9.5.5 Completion/Discontinuation of Subjects

A subject may elect to discontinue the study at any time for any reason. All subjects who discontinue the study are to complete the study's early discontinuation procedures indicated in the Schedule of Procedures/Assessments (Table 9).

The investigator or subinvestigator will promptly explain to the subject involved that the study will be discontinued for that subject and provide appropriate medical treatment and other necessary measures for the subject. A subject who has ceased to return for visits will be followed up by mail, phone, or other means to gather information such as the reason for failure to return, the status of treatment compliance, the presence or absence of AEs, and clinical courses of signs and symptoms.

Subjects who discontinue early from the study will be recorded on the CRF with the reason of discontinuation. Study disposition information will be collected on the Subject Disposition CRF.

9.5.6 Abuse or Diversion of Study Drug

Not applicable.

9.5.7 Confirmation of Medical Care by Another Physician

The investigator, subinvestigator, or clinical research coordinator will instruct subjects to inform site personnel when they are planning to receive medical care by another physician. At each visit, the investigator, subinvestigator, or clinical research coordinator will ask the subject whether he/she has received medical care by another physician since the last visit or is planning to do so in the future. When the subject is going to receive medical care by another physician, the investigator or subinvestigator, with the consent of the subject, will inform the other physician that the subject is participating in the clinical study.

9.6 Data Quality Assurance

This study will be organized, performed, and reported in compliance with the protocol, SOPs, working practice documents, and applicable regulations and guidelines. Site audits will be made periodically by the sponsor's qualified compliance auditing team, which is an independent function from the study team responsible for conduct of the study.

9.6.1 Data Collection

Data required by the protocol will be collected on the CRFs. As defined by GCP, the CRF is a printed, optical, or electronic document designed to record all of the protocol-required information to be reported to the sponsor on each study subject.

Data collection on the CRF must follow the instructions described in the CRF Completion Guidelines. The investigator has ultimate responsibility for the collection and reporting of all clinical data entered on the CRF. The investigator must sign the completed CRF to attest to its accuracy, authenticity, and completeness.

Completed, original CRFs are the sole property of the sponsor and should not be made available in any form to third parties without written permission from the sponsor, except for authorized representatives of the sponsor or appropriate regulatory authorities.

9.6.2 Clinical Data Management

All software applications used in the collection of data will be properly validated following standard computer system validation that is compliant with all regulatory requirements. All data, both CRF and external data (eg, laboratory data), will be entered into a clinical system.

9.7 Statistical Methods

All statistical analyses will be performed after the data cutoff for primary analysis or the study is completed, and the database is locked. Statistical analyses will be performed using SAS software or other validated statistical software as required. Details of the statistical analyses will be included in a separate statistical analysis plan (SAP).

9.7.1 Statistical and Analytical Plans

The statistical analyses of the study data are described in this section. Further details of the analytical plan will be provided in the SAP, which will be finalized before database lock.

9.7.1.1 Study Endpoints

The endpoints of this study are shown below. All efficacy endpoints will be assessed using mRECIST. If necessary, RECIST1.1 will also be performed and used for analysis.

9.7.1.1.1 PRIMARY ENDPOINTS

- DLTs (Part 1 only)
- Safety endpoints including AEs, laboratory tests, vital signs, ECG, ECOG-PS, and LVEF

9.7.1.1.2 SECONDARY ENDPOINTS

- **ORR** is defined as the proportion of subjects who have BOR of CR or PR
- Pharmacokinetic parameters of lenvatinib and nivolumab

9.7.1.1.3 EXPLORATORY ENDPOINTS

CCI

9.7.1.2 Definitions of Analysis Sets

DLT Analysis Set will include all subjects (Part 1 only) who have completed Cycle 1 without major protocol deviation with at least 75% of lenvatinib compliance and at least 2 doses of nivolumab and are assessed for DLT, and subjects who have experienced DLT during Cycle 1. This will be the analysis set to determine tolerability.

Safety Analysis Set will include all subjects who received at least 1 dose of lenvatinib or nivolumab.

PK Analysis Set will include all subjects who have received at least 1 dose of lenvatinib and nivolumab, and have evaluable concentration data.

The Efficacy Analysis Set will include all subjects who received at least 1 dose of lenvatinib and nivolumab.

The Pharmacodynamic and PGx Analysis Set is the group of subjects who received at least 1 dose of lenvatinib and nivolumab and had at least 1 postdose pharmacodynamic or PGx data.

9.7.1.3 Subject Disposition

Subjects who signed informed consent, failed screening and the reason for screen failures will be presented. Subjects who were treated, were not treated, completed the study, and discontinued the study and the reason for discontinuation will be presented. Similarly, subjects who completed the treatment, the reason for completion, discontinued the study treatment and the reason for discontinuation will be presented.

In this protocol, subjects who completed the study are defined as subjects who completed the appropriate DLT evaluation in Part 1 and subjects who completed the discontinuation assessment or last observation assessment in Part 2. Subjects who completed the study treatment are defined as who discontinued the treatment due to disease progression or subjects who are continuing the study treatment at the date of data cutoff.

9.7.1.4 Demographic and Other Baseline Characteristics

Demographic and other baseline characteristics for the Safety Analysis Set will be summarized for each part. Continuous demographic and baseline variables include age, height, and weight; categorical variables include sex, age group (<65 years, \geq 65 years), race, ethnics, ECOG-PS, and primary disease characteristics and prior therapies for primary disease.

9.7.1.5 Prior and Concomitant Therapy

All investigator terms for medications recorded in the CRF will be coded to an 11-digit code using the World Health Organization Drug Dictionary (WHO DD). The number (percentage) of subjects who took prior and concomitant medications will be summarized on the Safety Analysis Set by part. Anatomical Therapeutic Chemical (ATC) class (eg, anatomical class, therapeutic class, pharmacologic class, chemical class, if feasible), and WHO DD preferred term. Prior medications will be defined as medications that stopped before the first dose of study drug. Concomitant medications will be defined as medications that (1) started before the first dose of study drug and were continuing at the time of the first dose of study drug, or (2) or, started at the time of or after the first dose of study drug up to 30 days after the subject's last dose. All medications will be presented in subject data listings.

9.7.1.6 Efficacy Analyses

Efficacy analyses will be conducted by part based on the Efficacy Analysis Set. Tumor assessment will be analyzed based on the investigator's assessment. If needed, the analysis based on independent review will be conducted.

Part 1

BOR will be summarized based on mRECIST, and ORR and their corresponding exact 2-sided 95% confidence interval (CI) will be calculated. DCR and CBR will be summarized in a same manner.

Part 2

In addition to the same analysis as above for Part 1, PFS will be summarized and plotted over time by Kaplan-Meier method. The median, first and third quartiles (Q1 and Q3) of PFS rate and the cumulative probability of PFS rate at selected time points with 2-sided 95% CI will be calculated, but not limited to. PFS censoring rules will be defined in the SAP and followed FDA guidance (2007). TTP, DOR, TTR, and OS will be summarized similarly. A waterfall plot will be presented for the percent changes from baseline in the sum of the diameters of target lesions at post-baseline nadir (ie, maximum tumor shrinkage). A spider plot will be presented for the percent changes from baseline in the sum of the diameters of target lesions.

9.7.1.7 Pharmacokinetic, Pharmacodynamic, Pharmacogenomic, and Other Biomarker Analyses

9.7.1.7.1 PHARMACOKINETIC ANALYSES

The primary PK parameters of lenvatinib in the combination will be calculated by noncompartmental analysis using the PK analysis set (Part 1 only). If warranted, additional analyses may be performed. PK data for lenvatinib and nivolumab is planned to be analyzed using nonlinear mixed effects modeling. PK data for lenvatinib and nivolumab may also be used to explore the exposure-response relationships for antitumor activity/efficacy as well as biomarkers and safety, if feasible. The results of these analyses, if performed, will be reported separately.

9.7.1.7.2 PHARMACODYNAMIC, PHARMACOGENOMIC, AND OTHER BIOMARKER ANALYSES

The effect of lenvatinib-nivolumab combination therapy on soluble and/or tissue biomarkers will be summarized using descriptive statistics.

9.7.1.8 Safety/Tolerability Analyses

All DLT analyses will be performed on the DLT Analysis Set. The number and percentage of subjects with DLT will be calculated. DLT will also be summarized per type of toxicity. All other safety analyses will be performed on the Safety Analysis Set by part. Safety data will be summarized using descriptive statistics (eg, n, mean, standard deviation, median, minimum, maximum for continuous variables; n [%] for categorical variables).

9.7.1.8.1 EXTENT OF EXPOSURE

The number of cycles/days on treatment, sum of subject-time, number of administration, total amount of study drug administered, dose intensity, and relative dose intensity (actual dose/planned dose) will be summarized for lenvatinib and nivolumab separately.

9.7.1.8.2 ADVERSE EVENTS

The AE verbatim descriptions (investigator terms from the CRF) will be classified into standardized medical terminology using MedDRA. Adverse events will be coded to the MedDRA lower level term (LLT) closest to the verbatim term. The linked MedDRA preferred term (PT) and primary system organ class (SOC) are also captured in the database.

A treatment-emergent adverse event (TEAE) is defined as an AE that emerges during treatment and until the 30 days after the last dose or until the subject initiates new anticancer therapy, whichever is earlier, having been absent at pretreatment (Baseline) or

- Reemerges during treatment, having been present at pretreatment (Baseline) but stopped before treatment, or
- Worsens in severity during treatment relative to the pretreatment state, when the AE is continuous.

Only those AEs that are treatment-emergent will be included in summary tables. All AEs, treatment-emergent or otherwise, will be presented in subject data listings.

The incidence of TEAEs will be reported as the number (percentage) of subjects with TEAEs by MedDRA SOC and PT. A subject will be counted only once within an SOC and PT, even if the subject experienced more than 1 TEAE within a specific SOC and PT. The number (percentage) of subjects with TEAEs will also be summarized by highest CTCAE grade.

The number (percentage) of subjects with treatment-related TEAEs will be summarized by SOC and PT. Treatment-related TEAEs include those events considered by the investigator to be related to study treatment. The number (percentage) of subjects with treatment-related TEAEs will also be summarized by highest CTCAE grade.

The number (percentage) of subjects with TEAEs leading to death will be summarized by MedDRA SOC and PT. A subject data listing of all AEs leading to death will be provided.

The number (percentage) of subjects with treatment-emergent serious adverse events (SAEs) will be summarized by MedDRA SOC and PT. A subject data listing of all SAEs will be provided.

The number (percentage) of subjects with TEAEs leading to discontinuation of study drug, study drug dose reduction, and study drug interruption will be summarized by MedDRA SOC and PT. A subject data listing of all AEs leading to discontinuation of study drug, study drug dose reduction, and study drug interruption will be provided.

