9.4.7.2 Prohibited Concomitant Therapies and Drugs

Subjects should not receive other antitumor therapies while on study. If a subject receives additional antitumor therapies, this will be judged to represent evidence of disease progression, and continuation of the study medication and further participation in the study must be discussed and agreed upon with the sponsor.

Any live/attenuated vaccine (eg, varicella, zoster, yellow fever, rotavirus, oral polio and measles, mumps, rubella [MMR]) are prohibited during treatment and until 30 days post last dose.

The following medications are prohibited during the study. During DLT evaluation in Part 1, preventive administration or changes in dose or medication should be prohibited until occurrence of a DLT.

- Antiplatelet agents and anticoagulants that require INR monitoring, such as warfarin (treatments that do not require INR monitoring, such as low molecular weight heparin and certain factor X inhibitors are permitted).
- Immunosuppressive agents (except to treat a drug-related adverse event)
- Systemic corticosteroids > 10 mg daily prednisone equivalent.

Note: Following corticosteroids are allowed to use during the study.

- Topical, ocular, intra-articular, intranasal, and inhalational corticosteroids (with minimal systemic absorption)
- Adrenal replacement steroid doses >10 mg daily prednisone equivalent in the absence of active autoimmune disease.
- Immunosuppressive doses of corticosteroids to treat adverse events (> 10 mg daily prednisone equivalent)
- A brief course of corticosteroids (<3 weeks) for prophylaxis (e.g., contrast dye allergy) or treatment of non-autoimmune conditions (eg, delayed-type hypersensitivity reaction caused by contact allergen)

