9.5.1.5.1 ADVERSE EVENTS

An AE is any untoward medical occurrence in a subject. An AE does not necessarily have a causal relationship with the medicinal product. For this study, the study drugs are lenvatinib and nivolumab.

The criteria for identifying AEs in this study are:

- Any unfavorable and unintended sign (including an abnormal laboratory finding), symptom, or disease found after the time of informed consent, whether or not considered related to the investigational product (Note: Every sign or symptom should not be listed as a separate AE if the applicable disease [diagnosis] is being reported as an AE)
- Any new disease or exacerbation of an existing disease. However, worsening of the primary disease should be captured under efficacy assessments as disease progression rather than as an AE.
- Any deterioration in nonprotocol-required measurements of a laboratory value or other clinical test (eg, ECG or x-ray) that results in symptoms, a change in treatment, or discontinuation of study drug
- Recurrence of an intermittent medical condition (eg, headache) not present pretreatment (Baseline)
- An abnormal laboratory test result should be considered an AE if the identified laboratory abnormality leads to any type of intervention, withdrawal of study drug, or withholding of study drug, whether prescribed in the protocol or not

All AEs, regardless of relationship to study drug or procedure, should be collected beginning from the time the subject signs the study ICF through the 30 days after the last dose or until the subject initiates new anticancer therapy, whichever is earlier. SAEs will also be collected for 30 days after the last dose or until the subject initiates new anticancer therapy, whichever is earlier.

Any laboratory abnormality considered to constitute an AE should be reported on the CRF. Abnormal laboratory values should not be listed as separate AEs if they are considered to be part of the clinical syndrome that is being reported as an AE. It is the responsibility of the investigator to review all laboratory findings in all subjects and determine if they constitute an AE. Medical and scientific judgment should be exercised in deciding whether an isolated laboratory abnormality should be classified as an AE.

Abnormal ECG (QTcF) results, if not otherwise considered part of a clinical symptom that is being reported as an AE, should be considered an AE if the QTcF interval is more than

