8.3 Safety Data Handling

Treatment-emergent adverse event

A treatment-emergent adverse event (TEAE) is defined as an AE that emerges during the time from the first dose of study drug to 30 days following the last dose of study drug, having been absent at pretreatment (Baseline) or

- Reemerged during treatment, having been present at pretreatment but stopped before treatment, or
- Worsened in severity during treatment relative to the pretreatment state, when the AE was continuous.

Adverse Events

Adverse Events with incomplete start dates will be considered treatment emergent if:

- a. Day and month are missing and the year is equal to or after the year of the first dose date;
- b. Day is missing, and the year is after the year of the first dose;
- c. Day is missing and the year is equal to the year of the first dose date and the month is equal to or after the month of the first dose date;
- d. Year is missing;
- e. Complete date is missing.

Concomitant Medications

Medications with incomplete end dates will be considered concomitant if:

- a. Day and month are missing and the year is equal to or after the year of the first dose date;

- b. Day is missing, and the year is after the year of the first dose;
- c. Day is missing and the year is equal to the year of the first dose date and the month is equal to or after the month of the first dose date; or
- d. Year is missing;
- e. Complete date is missing.

OR; complete end dates is between the date of first study dose and date of last study dose even if the start date of medications is incomplete.

TEMAV (Treatment-Emergent Markedly Abnormal Value)

Treatment-emergent markedly abnormal laboratory value (TEMAV) is defined as a postbaseline laboratory value with grade 3 or higher, and with a grade increase from baseline. (ie., Increasing grade 0 to 3 or higher, grade 1 to 3 or higher, grade 2 to 3 or higher, grade 3 to 4 or 5, grade 4 to 5.)

Handling of below lower quantification values in laboratory results

In the cases where laboratory result contains below lower quantification (BLQ) value, it will be replaced to the lower limit value of quantification (LLOQ) for summary tables.

The priority of use for blood pressure

For systolic and diastolic blood pressures, additional confirmatory assessment will be done more than 60 minutes after initial assessment, if necessary. In the case where there are both the initial and confirmatory assessment results in a day, confirmatory one will be used.

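### AE, SAE and concomitant-therapy collection stops at new anticancer therapy, with no exception for a subject still taking study drug

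*Protocol*

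**What the plan says.** Several protocol rules share one cut-off. Section 9.5.1.5.1 has all AEs collected from consent "through the 30 days after the last dose or until the subject initiates new anticancer therapy, whichever is earlier", and adds: "SAEs will also be collected for 30 days after the last dose or until the subject initiates new anticancer therapy, whichever is earlier". Section 9.5.4.1 repeats the rule: SAEs, whatever their causality, "must be collected through 30 days after last dose or until the subject initiates new anticancer therapy, whichever is earlier". Section 9.4.7 records concomitant medication and therapy up to the same point. Section 9.7.1.8.2 sets the TEAE window in similar words: "emerges during treatment and until the 30 days after the last dose or until the subject initiates new anticancer therapy, whichever is earlier".

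On other antitumor therapy, 9.4.7.2 and the synopsis set a general rule: "Subjects should not receive other antitumor therapies while on study". They then provide for the subject who receives it anyway. It is taken as evidence of progression, and "continuation of the study medication and further participation in the study must be discussed and agreed upon with the sponsor".

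Three provisions set a different limit. Table 9 shows AEs and concomitant treatment recorded throughout. SAP 8.3 defines a TEAE as an AE that "emerges during the time from the first dose of study drug to 30 days following the last dose of study drug", with no cut at new therapy. Section 9.5.4.1 keeps one category open, with no time limit: "Any SAE judged by the investigator to be related to the study drug or any protocol-required procedure should be reported to the sponsor regardless".

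**The concern.** A cut at new anticancer therapy is harmless when that therapy begins after the last dose of study drug: it stops later toxicity of another regimen from being attributed to this one. The rules do not say that this is the only case they cover. Section 9.4.7.2 foresees a subject who has received other antitumor therapy and remains on lenvatinib and nivolumab. For that subject the earlier of the two dates falls in the middle of dosing.

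AEs are part of the primary endpoint (9.7.1.1.1), and TEAEs are tabulated regardless of causality. A site that follows the collection rules literally would stop recording non-serious AEs of any grade, and SAEs it judges unrelated, in someone still receiving the investigational combination. The SAP window would stay open over that time, and the absence of records would look like an absence of events.

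**Working it through.** **Where each window ends.** Let T be the start of the other antitumor therapy and L the last dose of study drug. The collection rules end at the earlier of T and L + 30 days. If T falls after L, the cut affects only the follow-up tail. In the 9.4.7.2 case T falls before L, so collection ends at T. The uncollected stretch is then (L − T) days of dosing plus the 30 days after it.

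| Provision | End point when T falls before L |
|---|---|
| 9.5.1.5.1, new AEs | T |
| 9.5.1.5.1 and 9.5.4.1, SAEs | T, but related SAEs reportable without time limit |
| 9.4.7, recording of concomitant therapy | T |
| 9.7.1.8.2, protocol TEAE | T, or not before L, depending on the reading |
| 9.5.1.5.1, follow-up of AEs already recorded | L + 30 days or resolution, whichever is first |
| 9.7.1.5, concomitant-medication analysis | L + 30 days |
| Table 9, AEs and concomitant treatment | Throughout |
| SAP 8.3, TEAE (both SAP versions in the file) | L + 30 days |

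Two further places suggest what was meant. Section 9.5.4.2 shortens the pregnancy window when new therapy starts, but counts the shortened window from the last study treatment, so it cannot close during dosing. Section 9.1.3.3 and Table 9 footnote q place the new agent after study drug has stopped. The AE clause appears to have been written for that setting without saying so.

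**The plan's own figure.** Protocol 9.7.2 gives the probability of at least one intolerable treatment-related AE in 20 subjects. The formula is 1 − (1 − p)^20.

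- p = 10%: 1 − 0.90^20 = 0.8784 (stated 87.8%)
- p = 15%: 1 − 0.85^20 = 0.9612 (stated 96.1%)
- p = 20%: 1 − 0.80^20 = 0.9885 (stated 98.8%)

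All three reproduce.

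**Effect of the cut, under assumptions.** The documents do not say how many subjects would be affected. Assume that k of 20 have collection closed while on drug, and that a fraction f of their event probability falls after closure. The probability becomes 1 − (1 − p)^(20 − k) × (1 − p(1 − f))^k. For k = 1, f = 0.5, p = 0.10 this is 1 − 0.90^19 × 0.95 = 0.8717.

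| k, f | p = 10% | p = 15% | p = 20% |
|---|---|---|---|
| 0 | 0.8784 | 0.9612 | 0.9885 |
| 1, 0.5 | 0.8717 | 0.9578 | 0.9870 |
| 2, 0.5 | 0.8645 | 0.9541 | 0.9854 |
| 4, 0.5 | 0.8491 | 0.9456 | 0.9815 |
| 4, 1.0 | 0.8147 | 0.9257 | 0.9719 |

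The last row is an extreme. Because the stated figure concerns treatment-related AEs, and related SAEs remain reportable, the true loss on this measure would be smaller for any given k and f.

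**Dosing time, also assumed.** If 1 to 3 of about 26 subjects continue for 2 to 6 further four-week cycles, the uncollected dosing is between 1 × 2 = 2 and 3 × 6 = 18 subject-cycles, that is 8 to 72 subject-weeks.

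**The case against.** The case against is substantial, and much of it stands.

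- **Counting.** A reader might infer that on-treatment toxicity is left out of the primary safety endpoint. The documents do not support that. SAP 5.6.3 builds the summary tables from the SAP 8.3 definition, which would count any such event that is recorded.
- **Listings.** It is tempting to add that events drop out of the listings. Section 9.7.1.8.2 lists all AEs, treatment-emergent or not, so an event is missing only if it was never collected.
- **Exposure.** One might argue that incidence is biased downward because dosing time still accrues as exposure. Incidence here is the number and percentage of subjects, each counted once per SOC and PT. No exposure-adjusted AE rate is planned, so subject-time is never the denominator.
- **Protocol TEAE wording.** The definition opens with events during treatment, and the cut can be read as governing only the tail. That is fair, and makes the definition ambiguous rather than wrong. The collection sentences in 9.5.1.5.1 and 9.5.4.1 have no such opening.
- **Rarity.** Other antitumor therapy is prohibited. If given, it counts as progression, itself a discontinuation criterion (9.3.3.1, item 5), so staying on drug needs the clinical-benefit exception and sponsor agreement. Treatment beyond progression alone involves no new therapy and is not a separate route. The case is therefore exceptional, but the protocol provides for it.
- **Terminology.** Section 9.4.7.2 speaks of additional antitumor therapy and the windows of new anticancer therapy. Neither term is defined. If a distinction is intended, it has to be stated.

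**Conclusion.** The point holds in a limited form. Followed literally, the protocol stops AE, SAE and concomitant-therapy collection during dosing in a subject who continues study drug under 9.4.7.2. What is lost is new non-serious AEs and new SAEs judged unrelated. Related SAEs remain reportable, and no section ends laboratory, vital-sign, ECG, ECOG-PS or LVEF data at new therapy. The rule conflicts with Table 9 and leaves the SAP 8.3 window open over time when AEs are not being collected.

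The size rests on assumptions. With 1 to 4 of 20 subjects affected and half their event probability lost, detection at 10% incidence moves from 87.8% to between 87.2% and 84.9%. The actual number is unknown and probably small. The documents do not support the stronger conclusion that the primary safety endpoint is biased by design. This is a minor-priority gap in the collection rule, worth closing because the repair is short.

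**What to change.** State in 9.5.1.5.1, 9.5.4.1, 9.4.7 and 9.7.1.8.2 that the new-anticancer-therapy cut applies only after the last dose of both study drugs, meaning the later of the two last doses. AEs arising on or before that date are then always collected and counted. The clause should also say when the window closes for a subject whose other therapy began during dosing; 30 days after the last dose would match SAP 8.3 for that subject. Make SAP 8.3 consistent with the amended text, and flag in the AE listing those events that start after on-treatment antitumor therapy. Aligning the SAP to the present wording of 9.7.1.8.2 would instead carry the ambiguity into the analysis.

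The cost is one clause in four protocol sections and an edit to SAP 8.3. No visits are added, since the subject is still attending for treatment. Under 11.1 the amendment may need IRB approval if it is judged to affect safety or scientific quality. A few AEs caused by the other therapy would enter the tables; the listing flag identifies those that may be.
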